8. DEMOGRAPHICS AND BASELINE CHARACTERISTICS

The demographics and baseline characteristics will be summarized for the ITT population. Individual subject listings will be provided to support the summary tables.

8.1. Demographics

Summary statistics will be provided descriptively by treatment group and total for the following continuous variables:

- Age
- Weight (kg)
- Height (cm)
- Body mass index (BMI; kg/m²)

Age or date of birth will be recorded on eCRF. Where age is not recorded, age will be calculated as described in Section 18.1.1.

Body mass index will be calculated as follows: BMI (kg/m²) = baseline weight in kg / (height in m)².

A frequency summary (number and percentage) will be provided by treatment group for the following categorical variables:

- Age category (≤ 32 years, $> 32 - \leq 50$ years and > 50 years)
- Sex (Male, Female with or without childbearing potential, Unknown, Undifferentiated)
- Race (American Indian or Alaska Native, Asian, Black or African American, Native Hawaiian or Other Pacific Islanders, White, Not Collected or Reported, Other)
- Ethnicity (Hispanic or Latino, Not Hispanic or Latino, Not Reported, Unknown)
- Region (North America and Europe, Middle East, Asia-Pacific)
- BMI category (< 20 , ≥ 20 to < 25 , ≥ 25 to < 30 , ≥ 30 kg/m²)

8.2. Baseline Characteristics

The following baseline characteristics will be summarized.

- Beta-thalassemia diagnosis: Beta-Thalassemia, Hemoglobin E/Beta-Thalassemia, Beta-Thalassemia combined with Alpha-Thalassemia;
- Baseline hemoglobin level (mean of at least 2 Hb values by central lab at least 1 week apart during the 28 days screening period) summarized as continuous variable as well as by category (≥ 8.5 g/dL and < 8.5 g/dL) excluding the Hb values within 21 days following a transfusion;

- Baseline NTDT-PRO T/W Score (calculated over 7 days prior to Dose 1 Day 1 detailed in Section 18.3.1) summarized as continuous variable as well as by category (≥ 3 points and < 3 points);
- Baseline NTDT-PRO SoB Score (calculated over 7 days prior to Dose 1 Day 1 detailed in Section 18.3.1);
- Baseline transfusion burden in units/24 weeks before Dose 1 Day 1 (descriptive and categorized level: \leq median value and $>$ median value if baseline transfusion burden > 0);
- Baseline transfusion burden in units/12 weeks before Dose 1 Day 1 (descriptive and categorized level: \leq median value and $>$ median value if baseline transfusion burden > 0);
- Beta-thalassemia gene mutation grouping: Beta Allele 1 Mutation, Beta Allele 2 Mutation, Alpha Gene 1 Mutation, Alpha Gene 2 Mutation, Other Disease-related Mutations
- Eastern Cooperative Oncology Group (ECOG) performance status (0 or 1) at screening visit to assess how the disease affects subjects' daily activities: 0 = fully active, able to carry on all pre-disease performance without restriction; 1 = restricted in physically strenuous activity but ambulatory and able to carry out work of a light or sedentary nature, e.g., light housework, office work; A listing will be provided for ECOG data.
- Splenectomy: Yes/No;
- Baseline Serum Ferritin;
- Hepatitis B and C results;
- MRI liver iron content (LIC) (descriptive and categorized level: < 3 , ≥ 3 - ≤ 5 , > 5 - ≤ 7 , > 7 - ≤ 15 and > 15). The value of LIC will be either the value collected from eCRF or the value derived from T2*, R2* or R2 parameter depending on which techniques and software was used for MRI LIC acquisition. Please refer to Section 10.4.10 for more imputation details
- Bone mineral density DXA scan (BMDs and T-scores by location);
- Baseline 6-Minute Walk Test (6MWT);
- Baseline FACIT-F Fatigue Subscale (FS);
- Baseline SF-36 PCS and MCS Scores.

8.3. Beta-thalassemia Comorbidities/Medical History

The Beta-thalassemia comorbidities and medical history will be coded by Medical Dictionary for Regulatory Activities (MedDRA; Version 23.0), and summarized by system organ class (SOC) and preferred term (PT) by treatment group and total. Separate tables will be provided for current

Beta-thalassemia comorbidities and the history of Beta-thalassemia comorbidities. The SOCs and PTs will be listed in descending frequency within the luspatercept group. A subject will be counted only once for multiple events within each SOC/PT.

A separate table will be provided to summarize Beta-thalassemia comorbidities by comorbidity terms for each treatment group and total.

Corresponding listing will be provided. For cancer history, data will be presented in the listing.

[REDACTED]

[REDACTED]

[REDACTED]

[REDACTED]

[REDACTED]

[REDACTED]

[REDACTED]

[REDACTED]

[REDACTED]

[REDACTED]

[REDACTED]

[REDACTED]

[REDACTED]

9 STUDY TREATMENTS AND EXTENT OF EXPOSURE

Subjects will be assigned to one of following regimens during treatment phase:

- Luspatercept starting dose level 1.0 mg/kg SC once every 21 days
- Placebo SC once every 21 days

Study treatment and extent of exposure summaries will be provided based on the safety population. Descriptive statistics will be provided for treatment duration, number of doses received per subject/treatment and average number of days per dose by treatment group and total. The number and percentage of subjects will be summarized for maximum dose level received, and dose level reduced to by treatment group and total. Corresponding listing will be provided.

9.1 Treatment Duration

Treatment duration (weeks) is defined as:

$$\lfloor (\text{The treatment end date}) - (\text{The treatment start date}) + 1 \rfloor / 7,$$

where the treatment start date is the date of the first dose of study drug. The treatment end date is \min [(date of last dose + 20), death date]. For subjects who are still on treatment at the time of study closure or clinical cutoff, the minimum of (data cutoff date, date of last dose+ 20) will be used as the treatment end date.

Descriptive statistics will be summarized for treatment duration by treatment group and total.

9.2 Number of Doses Received per Subject

Total number of doses received per subject is defined as the total number of doses the subject received (i.e., total number of non-zero doses). It will be summarized descriptively and categorically (1, 2, 3, 4, 5, 6, 7, 8, 9 – 16, 17 – 24, 25 – 32, >32) by treatment group and total. The total number of doses received will be calculated from all subjects within each treatment group. The total number and percentage of doses received for each planned dose level (1.25 mg/kg, 1.0 mg/kg, 0.80 mg/kg, 0.60 mg/kg, 0.45 mg/kg) will be calculated within treatment group, with the total number of doses received as denominator.

9.3 Average Number of Days Between Doses

Average number of days between doses is defined as number of days on treatment (treatment duration) divided by the number of doses (where a subject received a non-zero dose) for each subject. Descriptive summary statistics will be provided for average number of days per dose by treatment group and total.

9.4 Dose Modifications: Dose Delay, Dose Titration and Dose Reduction

9.4.1 Dose Delay

Dose delay is defined as delay of planned dose schedule due to increased hemoglobin (≥ 11.5 g/dL) or adverse events which are also further categorized by related events equal to grade 2 and \geq grade 3 or WBC count $\geq 3X$ baseline or any other reasons. If dose delay exceeds 15 weeks from last dosing date, the treatment should be discontinued.

9.4.2 Dose Titration and Dose Reduction

Dose adjustment includes dose reduction and dose titration (increase). Titration is based on hemoglobin level over the previous two doses compared to baseline. Subjects may be dose-escalated up to 1.25 mg/kg during the DBTP and OLP, but the maximum total dose per administration should not exceed 120 mg. The dose escalation criteria are defined as follows:

- Dose escalation may be performed if at a constant dose level, the increase of mean hemoglobin (uninfluenced by transfusions, ie, > 21 days post-transfusion) over 2 cycles (6 weeks) is < 1.0 g/dL, compared to the baseline hemoglobin value (mean of 2 values 1 week apart within 4 weeks of randomization);
- Dose escalation may be performed if at a constant dose level, the increase of mean hemoglobin (uninfluenced by transfusions, ie, > 21 days post-transfusion) over 2 cycles (6 weeks) is ≥ 1.0 , but < 2.0 g/dL compared to the baseline hemoglobin value (mean of 2 values 1 week apart within 4 weeks of randomization).

Dose reduction can be caused by increased or high level of hemoglobin or adverse events. Subjects who have been dose-reduced due to any related AE \geq Grade 3, as indicated in Table 5 of Protocol, should not be dose-escalated during the DBTP. Although, following Investigator's requests, the Sponsor may allow dose increase to the next higher dose level, after safety and efficacy data review. Starting dose with dose reductions and escalations are presented in

Table 1.

Table 1: Starting Dose Level with Dose Adjustments

3rd Dose Reduction (~ 25 %)	2nd Dose Reduction (~ 25 %)	1st Dose Reduction (~ 25 %)	Starting Dose Level	1st Dose Increase
0.45 mg/kg	0.6 mg/kg	0.8 mg/kg	1.0 mg/kg	1.25 mg/kg

The dose delay, dose reduction, and dose titration will be summarized in separate tables by treatment group and total. The number of subjects with at least one dose delay/reduction/titration, number of dose delays/reduction/titration per subject, reason for dose delay and adjustment, time to first dose delay/reduction/titration (days), and time to first dose delay/reduction due to AE (days) will be summarized by treatment group and total. Corresponding listing will be provided.

9.5 Investigational Drug Overdose

Overdose (refers to luspatercept only), is defined as SC 10% over the protocol-specified dose level assigned to a given subject, regardless of adverse events or sequelae. A listing will be provided for any overdose, which occurs accidentally or intentionally as collected in the eCRF.

10 EFFICACY ANALYSIS

All efficacy evaluations will be conducted using the ITT population with the exception of FACIT-F Fatigue Subscale (SF) and SF-36 analyses that will be conducted on the HRQoL evaluable population. NTDT-PRO T/W and SoB scores will be analyzed by both ITT and HRQoL populations. The primary and key secondary endpoints will also be analyzed based on the Per Protocol population as a sensitivity analysis.

Some continuous variables like hemoglobin and weekly NTDT-PRO T/W and SoB domains will be derived as the sum of results over 12 weeks divided by the number of assessments. The mean over 12 weeks will be used to derive mean change from baseline for each subject.

For the early treatment-discontinued subjects, i.e. subjects who did not complete 24 weeks or 48 weeks of double-blinded treatment period, the transfusion and assessment records (including Hb and QoL) will still be collected up to 48 weeks post Dose 1 Day 1 or 9 weeks post last dose, whichever is the later date. All the assessments before the efficacy cutoff date will be used to evaluate primary and secondary endpoints. For these endpoints, if at the time of data summary, a subject has died or has not reached the end of the 12-week interval, this subject will be included in the analysis. For other efficacy endpoints, the collected records will be used (by visits or at specified time point) as needed, depending on the purpose of the summary. Please refer to the individual endpoint section for details.

The efficacy cutoff date is defined as the minimum date among death date, study discontinuation date, last dose date + 20, and data cutoff date. For the primary and responder-related secondary endpoints, if at the time of data summary, a subject's efficacy cutoff date is before the end of the 12-week interval or a subject has any invalid hemoglobin records (i.e., within 21 days following a transfusion) during the specified 12-week interval, this subject will be included in the analysis and his/her responder status will be classified in accordance with the definition of erythroid response in Section 10.2. For other efficacy endpoints, if a subject's efficacy cutoff date is before the end of the 12-week interval, the subject will be included in the analyses.

Statistical comparisons will be made between luspatercept and placebo. Key secondary efficacy results that will be considered statistically significant after consideration of the strategy for controlling the family-wise Type 1 error rate are described in Section 10.1. All statistical tests will be 2-sided at the significance level of $\alpha = 0.05$, and the corresponding p-values and 2-sided CIs for point estimates will be reported, unless specified otherwise.

In general, descriptive statistics will be provided and statistical tests will be applied if appropriate. For continuous variables, least squares (LS) means with corresponding standard errors (SE) for each treatment group, along with LS mean of treatment difference (luspatercept versus placebo) with corresponding 95% CI and p-value will be presented for analysis of covariance (ANCOVA). Counts and percentages will be used to describe categorical variables, and the treatment comparison will be analyzed analogous to the primary efficacy endpoint, using the CMH model

stratified by baseline randomization stratification factor(s). The odds ratio (OR) (luspatercept versus placebo) with corresponding 2-sided (at 0.05 alpha level) 95% CI and p-value will be provided. The difference in proportions (luspatercept – placebo) and 95% CI will also be calculated. A forest plot showing the ORs, 95% CI and p-value for the overall result and the results in each subgroup will be constructed for primary and key secondary endpoints. For all endpoints mentioned in this section, records beyond week 48 will not be used unless otherwise specified. If ANCOVA is used, the statistical assumption will be validated first, log transformation will be applied as needed.

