4.2.2. Secondary Efficacy Endpoints

4.2.2.1. Key Secondary Efficacy Endpoints

The analyses of secondary efficacy endpoints will be performed on the ITT population. The key secondary endpoints will be measured from Dose 1 Day 1 of the DBTP, and will be statistically tested in a sequential order at two-sided $\alpha = 0.05$ level (details related to multiplicity adjustment can be found in Section 10.1). The key secondary efficacy endpoints include:

- Mean change from baseline in NTDT-PRO Tiredness and Weakness (T/W) domain score over a continuous 12-week interval from Week 13 to Week 24.
- Mean hemoglobin change from baseline over a continuous 12-week interval from Week 13 to 24 in the absence of transfusion.
- Proportion of subjects who have an increase from baseline ≥ 1.0 g/dL in mean of hemoglobin values over a continuous 12-week interval from Week 37 to Week 48 in the absence of transfusions.

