 - c. Average of all Hb measurements in Weeks 14-25 (Day 93 to Day 176) if Weeks 14-25 has ≥ 3 Hb measurements
 - d. When the number of Hb measurements is less than 3 among Weeks 13-24, Weeks 12-23, and Weeks 14-25, then choose the largest number of Hb measurements in the following order as Hb at Week 13-24:
 - 1) Hb in Week 13-24
 - 2) Hb in Week 12-23

- 3) Hb in Week 14-25
 - e. Otherwise, missing
 - Weeks 37 - 48 interval: Same rule as Week 13-24 interval
- The calculation of weekly NTDT-PRO scores is detailed in Section 18.3.1. The 12-week interval score is obtained by averaging all the weekly scores (at least one non-missing) in these 12 weeks. If all the weekly scores in these 12 weeks are missing, the 12-week interval score is then declared missing.

This SAP addresses efficacy and safety endpoints during the double-blinded treatment period (including the initial 48-week treatment period for all subjects and the long-term treatment period for early enrolled subjects). The database will be locked upon all subjects completed 48 weeks of the double-blind treatment period or discontinued before reaching 48 weeks. All the data collected up to data cutoff date will be used for summary. Data selection rules will be applied in each summary panel as needed, please refer to individual part for details.

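### The last-dose-plus-20-days efficacy cutoff sets aside required off-drug Hb and NTDT-PRO values, so followed early stoppers fall out of, or are truncated in, the ITT-labelled T/W and Hb-change tests

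*SAP*

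**What the plan says.** SAP Section 10 sets the data rule. The "efficacy cutoff date is defined as the minimum date among death date, study discontinuation date, last dose date + 20" and the data cutoff date, and "All the assessments before the efficacy cutoff date will be used to evaluate primary and secondary endpoints". For a subject who has stopped IP, evaluable data therefore end no later than 20 days after the last dose.

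The same section says that for early stoppers the "records (including Hb and QoL) will still be collected up to 48 weeks post Dose 1 Day 1 or 9 weeks post last dose"; of these two dates, the later applies. The protocol asks for these data. Section 6.4 and Table 3 footnote 3 require Hb at Weeks 13, 19, 24, 37, 42 and 48 even off drug, and Section 6.8 requires a seven-day NTDT-PRO diary before Weeks 13, 24, 37 and 48. SAP 10.2, 10.3.2 and 10.3.3 each repeat that Hb collection continues in discontinued subjects.

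On missing values, SAP 10.6.1 and 10.6.2 make complete case the main analysis for Hb change and for T/W, and non-responder imputation the main analysis for the Hb responder endpoints. SAP 5.2.1 and 10.3 label the tests ITT. Section 10 adds, for endpoints other than the responder ones, that if the "efficacy cutoff date is before the end of the 12-week interval, the subject will be included in the analyses". It gives no value for such a subject.

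SAP 5.1 states that "All the data collected up to data cutoff date will be used for summary", then that "Data selection rules will be applied in each summary panel as needed, please refer to individual part for details". It accepts an interval mean built on a single weekly T/W score or on fewer than three Hb values.

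**The concern.** The plan collects off-drug values at exactly the weeks that define the Week 13–24 and Week 37–48 endpoints, then limits endpoint data to a date that most of those values fall after. A subject who stops IP early but attends every follow-up visit can be absent from a test labelled ITT, or be represented only by weeks on drug.

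The two tests most affected are gated. T/W at Weeks 13–24 is tested first after the primary and Hb change second. If T/W fails, key secondaries 2 and 3 are not tested (SAP 10.1). What the T/W test estimates should therefore be unambiguous.

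**Working it through.** **The plan's own figure.** SAP 4.4 gives T/W changes of 1.2 and 0.5, SD 1.2, 100 and 50 subjects, two-sided 0.05, power 91%. The noncentrality is 0.70 / (1.2 × √(1/100 + 1/50)) = 3.37, and a two-sample t test then has 91.7% power. With 90 and 45 subjects it has 88.7%. The stated figure is reproduced approximately and is not in dispute.

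**Calendar.** Dose k falls on Day 1 + 21(k − 1), so the cutoff is that day + 20 = Day 21k. Diary week w covers Days 7(w − 1) + 1 to 7w and normally needs at least 4 days (SAP 18.3.1). The Hb windows in SAP 5.1 are Days 86–169, then 79–162, then 93–176, then the largest count available. On-drug Hb is drawn on dosing days and on Days 8 and 15 of Dose 6 (Days 113 and 120).

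| Last dose | Cutoff day | Usable diary weeks, of 12 | Scheduled on-drug Hb usable for Weeks 13–24 |
|---|---|---|---|
| 1, 2, 3 | 21, 42, 63 | 0 | none |
| 4 | 84 | 0 | none, unless one is drawn on Days 79–84 |
| 5 | 105 | 3 | Day 85 only, through the Weeks 12–23 fallback |
| 6 | 126 | 6 | Days 106, 113, 120 |
| 7 | 147 | 9 | Days 106, 113, 120, 127 |
| 8 | 168 | 12 | Days 106, 113, 120, 127, 148 |

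**Limits of the table.** It assumes nominal days. Dosing visits may move by 3 days, and SAP 18.3.1 relaxes the diary rule to 2 days for subjects with no valid score in the interval. Dose 4 on Day 67 gives a cutoff of Day 87, so Days 85 and 86 can make Week 13 valid. Dose delays and extra Hb draws can also add on-drug values.

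**Consequence by endpoint.**
- T/W and Hb change: complete case removes subjects with no value. Those with last dose 5 to 7 enter on 3, 6 or 9 diary weeks, and on one to four scheduled Hb values.
- Primary and key secondary 3: a subject with no value is a non-responder and stays in the denominator. A truncated mean can still decide response; after Dose 5 it rests on the single Day 85 value.

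**Illustration for T/W.** The affected shares are assumed. The 10% dropout in SAP 4.4 is not defined as stopping IP while followed. Let d be the share per arm whose values are omitted and q the fraction of the change they keep off drug. Using their values, the difference is [(1 − d) + dq] × (1.2 − 0.5).

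| d | q | Difference, all values | Power, all values (100/50) | Power, complete case (difference 0.70) |
|---|---|---|---|---|
| 5% | 0 | 0.95 × 0.70 = 0.665 | 88.9% | 90.3% (95/47.5) |
| 5% | 0.5 | 0.975 × 0.70 = 0.683 | 90.4% | 90.3% |
| 10% | 0 | 0.90 × 0.70 = 0.63 | 85.3% | 88.7% (90/45) |
| 10% | 0.5 | 0.95 × 0.70 = 0.665 | 88.9% | 88.7% |

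With q = 1 the difference stays 0.70. With unequal shares and q = 0, the direction depends on the arm: 5% on luspatercept only gives 0.95 × 1.2 − 0.5 = 0.64, and 5% on placebo only gives 1.2 − 0.95 × 0.5 = 0.725.

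**What the omitted data would supply.** For last dose 1 to 3, the Week 13, 19 and 24 visits normally give about three Hb values. For T/W, the diary before Week 24 gives about one week. The diary before Week 13 nominally falls in Week 12, outside the interval.

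**The case against.** The strongest reply is that the SAP never says in words that later values are discarded, and that other text points to their use. SAP 5.1 defines the Hb interval with no dosing limit. The endpoint sections mention continued Hb collection while describing how the interval mean is formed. The three-value evaluability rule in SAP 10.2 matches the three mandated visits at Weeks 13, 19 and 24. This shows that the SAP needs reconciling, but it does not lift the cap: those sections say only that data are collected, and Section 5.1 defers data selection to the individual parts, where Section 10 imposes the cutoff.

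A second reply is that an on-treatment target was intended. The protocol summary counts Weeks 13 to 24 as weeks of treatment, and protocol 9.6.2.2 and SAP 10.3 tie Hb change to the treatment period. SAP 5.1 says "This SAP addresses efficacy and safety endpoints during the double-blinded treatment period", and SAP 4.2.2.1 says "The key secondary endpoints will be measured from Dose 1 Day 1 of the DBTP". One dosing interval after the last dose fits that reading. This stands in part. A reader might infer that the documents contain no on-treatment target at all; that goes too far. The wording is inconsistent, and it sits beside an ITT label.

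Third, the statement on inclusion may mean only that an early cutoff is not itself a ground for exclusion. That is a fair reading, but it should be written down.

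Fourth, sensitivity analyses exist: imputation (SAP 10.6), rules for fewer than three Hb values (SAP 10.2) and a repeated-measures Hb model (SAP 10.4.18). None is stated to use the observed off-drug values. A separate HRQoL SAP is not available here, so T/W sensitivity handling is not fully known.

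**Conclusion.** The point holds for key secondaries 1 and 2. As written, followed subjects with last dose 1 to 3 have no usable Week 13–24 value on nominal days, last dose 4 generally has none, and last dose 5 to 7 enters on a truncated on-drug mean. This does not fit the ITT label, and the target is worded inconsistently.

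Two stronger readings are tempting. A reader might infer that the primary result is compromised. The documents do not support that: non-responder imputation keeps subjects with no value in the denominator, which is conservative for a responder rate. A reader might also infer bias in favour of luspatercept. The documents give neither a rate of stopping IP while followed nor an off-drug course, so size and direction are unknown. In the illustration with equal shares, complete-case power exceeds all-values power by 1.5 or 3.4 points if no benefit is kept, and the gap is about zero if half is kept.

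This should be fixed because it concerns gated tests and uses data already required. Confidence is medium.

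**What to change.** In SAP Section 10, for the ITT analyses of key secondaries 1 and 2, and for the primary and key secondary 3 for consistency, set the efficacy cutoff to the earliest of death, study discontinuation and data cutoff. Use every Hb and NTDT-PRO value collected in the window, whether or not IP was stopped. Keep last dose + 20 days as a labelled on-treatment sensitivity analysis and for the rolling and duration-of-response analyses.

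If an on-treatment main target is intended, say so and prespecify the all-collected-data analysis as a sensitivity analysis. In either case, state in one sentence what the ITT tests estimate, and reconcile Section 10 with Sections 5.1, 10.2, 10.3.2, 10.6.1 and 10.6.2.

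The cost is SAP text and programming; no new data are needed. The downsides are:
- The estimated effect may be slightly smaller.
- T/W for the earliest stoppers may rest on about one off-drug diary week. Last dose 3 or 4 could have two, but only if the visit 9 weeks after last dose includes a seven-day diary, which the protocol leaves unclear. A late Week 24 visit could move its diary past the interval.
- Off-drug values may reflect later therapy.
- Nothing is recovered for subjects who leave the study.
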